For the study we will recruit participants from the community. Information needed to determine whether research participant meets eligibility requirements will be obtained during an initial phone-screen (see attached – using questions drawn from the Mini International Neuropsychiatric Interview (MINI)). If research participants meet the inclusion criteria based on the phone screening, they will be scheduled for an in-person or remote initial clinical assessment. Trained assessors will go through each criterion and document whether the research participant is eligible for the study using a standardized assessment checklist. If research participants meet the inclusion criteria based on the clinical assessment, they will be scheduled for an in-person or remote clinical intake. Research participants will be included if they meet the following criteria:

Individuals will be included if they:

1. Are 18 to 70 years old
2. Have experienced 12 or more loss of control episodes within the previous 3 months
3. Have a BMI above 18.5
4. Are located in the US and willing/able to participate in remote treatment
5. Are able to give consent

Individuals will be excluded from the study if they:

1. Are unable to fluently speak, write and read English
2. Are already receiving treatment for an eating disorder (e.g., research participants cannot be receiving concurrent eating disorder treatment from another provider)
3. Have a mental handicap or are currently experiencing severe psychopathology that would limit their ability to engage in study (e.g., suicidality, substance use disorder, active psychotic disorder, severe depression with suicidal intent)
4. Are purging and/or using laxatives 3 or more times per week and are not deemed safe for outpatient treatment by a primary care provider
5. Are unwilling to receive medical clearance and/or medical monitoring as requested by the study to ensure they are medically safe to participate
6. Are pregnant or planning to become pregnant within the next year
7. Are individuals who are not yet adults (infants, children, teenagers)
8. Are currently taking any of these medications: Haldol, Loxitane, Mellaril, Moban, Navane, Prolixin, Serentil, Stelaxine, Trilafon, Thoraxine, Abilify, Clozaril, Geodon, Risperdal, Seroquel, Zyprexa
9. Are adults unable to consent

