Addition of intervention factors to self-help CBT program to accomplish factorial design. As mentioned above, participants will be randomized to one of the 4 treatment combinations. The standard of care for binge spectrum eating disorder and bulimia nervosa is behavioral treatment. In this project, all the participants will receive self-help CBT program based on [name] evidence-based treatment program for binge spectrum eating disorders, and is superior to standard of care. As such, there is no potential of randomizing subjects into a condition that is less than standard of care for their eating disorders. Below, we describe the treatment when each of the two intervention factors are turned ON and OFF and when synergies occur between both intervention factors, as applicable.

Advanced Digital Data Sharing with Coaches When Advanced DDS with Coaches is turned ON, coaches having a bachelor's degree in health-related fields (e.g., psychology, nursing, nutrition etc.) will have access to a secure web portal called the digital data portal. Our team has successfully developed and used a digital data portal for ED treatments in a recent CBT+ clinical trial (R34MH11602). This portal will accomplish four key functions including, 1) gather data on target behaviors from the base self-help app (i.e., uptake of weekly module, self-monitoring compliance and skills utilization), 2) synthesize participants' behavioral data on treatment targets, 3) flag data to increase salience of behaviors needing improvement and 4) use sophisticated algorithms to generate recommendations for intervening on the identified data patterns. Using the information from the digital data portal, the coaches will send weekly emails to facilitate improvement in treatment targets. Coaches will send one email a week for a total of 12 emails over the course of treatment.

When Advanced DDS with Coaches is turned OFF, participants' will not have their data shared and will not receive emails from the coaches.

Just-in-time, adaptive interventions (JITAI) The proposed JITAI system will use machine learning algorithms to intervene on 1) treatment adherence, and 2) skills utilization during the 12 weeks of treatment. When JITAI are turned ON, the base self-help app will be used to deliver targeted, personalized and automated interventions during machine learning

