Patients with frequent or and intense eating disorder pathology, or medical symptoms related to their eating disorder must receive clearance from their primary care physician (PCP) before they can be considered eligible for participation in this study. PCPs will be asked to provide measurements of height, weight, vital signs, and blood draws. PCPs will be notified via letter of their role in determining eligibility for the study and will be provided contact information for the study PI if they have any questions or concerns. Individuals who are or become medically unstable for outpatient treatment will be referred for appropriate medical treatment. Patients must also agree to allow study staff to communicate with their PCP throughout the study and to be reassessed for medical stability if there is a worsening in symptoms. Once a participant is enrolled in the study, study therapists/staff and the PCP will jointly determine the appropriate level of medical care outside of study visits to ensure the participant remains medically stable for outpatient treatment. If patients become medically unstable for outpatient treatment or show a significant and continued worsening in symptoms, they will be removed from the study and referred to a higher level of care. The procedures for medical management of the study patients described above have been successfully utilized by our lab in prior studies of patients with binge eating spectrum disorders. After potential participants are deemed eligible a baseline assessment will be completed. If participants are found to be ineligible at any stage of the process, participants will be given referrals if desired.

Following the baseline assessment, participants will be randomized to receive one of the four treatment conditions and will receive 12 weeks of treatment.

Plans for assessing and/or intervening on suicidal ideation or risk for serious self-harm.

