Participants will continue in their current medical treatment at time of enrollment. Medical status will be closely monitored throughout the intervention. Participants will be required to sign consent to contact their PCP throughout the study to ensure coordination in care. The PCP will be provided with a letter describing enrollment in the study. Participants will be informed that the research team will inform the PCP if there is a change in symptom status such as notable weight loss, increase in restrictive eating behavior or increase in purging behavior that may require additional medical management. Concurrent psychotherapy for eating pathology will not be permitted during the study as this could confound data. Pharmacological management will be permitted for psychiatric co-morbidities. Any prescribed medications or dosage changes will be carefully tracked through the study.

Assessment Procedure. Assessments will occur at at baseline, mid-treatment, post-treatment, and at 3-month follow-up. In order to maximize assessment completion, we

PROTOCOL TITLE: Using factorial design to examine efficacies of technology-based augmentations for improving treatment adherence and skills utilization in a self-help CBT program for binge eating.

Protocol Version Date: April 19, 2022

will increase compensation across assessments (\$20, \$30, \$50 and \$75). At the beginning of the assessment at the baseline, the assessor will review the IRB approved Consent Form with the prospective participant. Of note, none of the assessments within the proposed study requires prospective participants to provide their signatures except for the Consent Form. Assessments will be conducted by Independent Evaluators (IEs), IEs will be trained until they reach 100% agreement on diagnosis and acceptable reliability (>.80) on EDE scoring. Assessments will be audio recorded for review. Twenty randomly selected tapes will be reviewed to compute reliability statistics. All measures listed below have acceptable psychometric properties.

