Assessments will be conducted by unblinded assessors at baseline, mid-treatment, post-treatment, and at 3-month follow-ups. Assessments will be for a total of 3 hours in length. Assessors for the baseline, mid-treatment, post-treatment, and 3 month follow up will be research coordinators employed and paid by the WELL Center and Ph.D students at Drexel University. Three hours of the assessment is a semi-structured interview in which the participants will be using a zoom link via Drexel's HIPAA compliant Zoom platform the assessor sent prior to the interview to meet with the assessor who conducts the interview with the participant. Total length of participation in this study will be about 7 months from the baseline assessment to the 3-month follow-up assessment. As the study continues, the status of the trial will be updated on <http://www.ClinicalTrials.gov> as different phases of the study start and end (including but not limited to “not yet recruiting”, “recruiting”, “active not recruiting”, and “completed”).

This study will have 2 kinds of blind assessors. One type of blind assessor is the study coordinator. The study coordinator is a full-time paid employee on the study. As part of their job responsibilities, they will conduct assessments for this current study. The other type of assessors is graduate students. Students serve as assessors on clinical trials being conducted in a research lab to receive specialized training and supervision in conducting clinical interviews for assessing eating disorders. Typically, graduate students are obligated to fulfill 8 hours of training time in the specialized research lab without getting paid. Graduate students will be asked to conduct assessments within these 8 hours of free lab time and hence, will not be paid for conducting the assessments. In the conditions with Advanced DDS with Coaches, coaches will be unblinded throughout the 12-week program. Coaches will know the study condition and diagnosis of the specific patients they've been assigned in order to facilitate improvement in treatment targets of the patients they've been assigned. Coaches will be blinded to the clinical outcomes from treatment for the patients they are assigned to. They will be blinded to all clinical outcomes data collected at different assessment time points.

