safeguard participants' data and privacy, in treatment conditions when JITAs are turned ON, following steps will be taken. 1) Intervention messages will only be accessible via smartphone app which will be password protected, 2) Intervention messages will be nondescript and will not include participant's PHI including information pertaining to mental health diagnosis or treatment, and 3) Push notifications will not contain any sensitive information.

13) Provisions to Monitor the Data to Ensure the Safety of Subjects

Participants will continue in their current medical treatment at the time of enrollment. Medical status will be closely monitored throughout the intervention. Participants will be required to sign consent to contact their PCP throughout the study to ensure coordination in care. The PCP will be provided with a letter describing enrollment in the study. Participants will be informed that their study staff will inform the PCP if there is a change in symptom status such as notable weight loss, increase in restrictive eating behavior, or increase in purging behavior that may require additional medical management. If the study team becomes aware of worsening levels of disordered eating symptoms that could pose an acute danger to the research participant's health, we will work with them to get touch with their primary care physician and encourage additional medical monitoring to ensure they are safe and stable enough to be receiving outpatient treatment based on their primary care physician's discretion. If they do not have access to a primary care physician, we will help them locate one. We will also provide referrals for treatment. Concurrent psychotherapy will not be permitted during the study as this could confound data. Pharmacological management will be permitted for psychiatric comorbidities. Any prescribed medications or dosage changes will be carefully tracked through the study.

14) Withdrawal of Subjects

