Research participants will be withdrawn from the study if they no longer meet the study criteria and/or they experience any acute life-threatening incident (precipitous drop in weight, change in electrolyte balance, etc.), hospitalization, suicidal or homicidal ideation, or serious self-harm behavior, failure to comply with study procedures. Condition of pregnancy will be assessed during the baseline, mid-treatment, post-treatment, and 3 month follow-up. If the research participant finds out that they are pregnant or plan on becoming pregnant within the next year during their time in the study, they must notify the project coordinator immediately. They will no longer meet study criteria and will be withdrawn from the study immediately. If termination is found necessary, the research participant will be contacted by the project coordinator immediately and the necessary precautions will be taken to ensure safety or medical attention as appropriate. The research participant will then be provided with referrals to other programs or studies if applicable and the data will be destroyed/banned from use. If, at any time, the treating physician determines that the health of the research participant precludes continuation of outpatient treatment, a meeting will be scheduled with the treating physician, research participant, and study staff to assist in locating referrals for appropriate levels of care. If a higher level of care is sought, research participants will be removed from the trial. Research participants are given the option to be added to our study database to be contacted for other studies they

PROTOCOL TITLE: Using factorial design to examine efficacies of technology-based augmentations for improving treatment adherence and skills utilization in a self-help CBT program for binge eating.

Protocol Version Date: April 19, 2022

might be eligible for at the WELL Center in the future. If they choose not to be entered into the database, all their information will be destroyed.

15) Risk to Subjects

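### Worsening, moving to higher care and non-compliance end participation in the study, not only in treatment, so outcomes can be lost because of a poor course; the effect is probably small and the repair is cheap

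*Protocol*

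**What the plan says.** Three rules end participation in the study itself.

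- **Continued worsening.** Protocol section 10, in the screening text on medical clearance, says of enrolled patients who become medically unstable or "show a significant and continued worsening in symptoms, they will be removed from the study and referred to a higher level of care".
- **Higher level of care.** Sections 14 and 15 describe a treating physician deciding that outpatient treatment cannot continue, then a meeting about referral, and then: "If a higher level of care is sought, research participants will be removed from the trial".
- **Non-compliance.** Section 14 lists failure to comply with study procedures among the grounds for withdrawal, beside acute medical events, hospitalization, suicidal or homicidal ideation and serious self-harm.

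Section 14 also says that when a termination is necessary, the data are destroyed or barred from use. Its last sentence destroys all information on people who decline the contact database.

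Two passages soften this. Section 24 encourages people who discontinue treatment to keep attending assessments. Section 15 keeps mild, transient worsening enrolled and sends sustained worsening to a consultation with the primary care physician.

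The SAP (Statistical Design and Power) plans likelihood methods and multiple imputation. It adds sensitivity analyses if missingness is related to the missing outcome. It does not mention the removal rules.

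**The concern.** Worsening of eating-disorder symptoms lies close to the outcomes themselves, binge eating frequency and EDE global score. A rule that ends assessment because of worsening makes the chance of a missing value depend on how badly the person is doing. The contrasts at post-treatment and 3 months (Aim 3) and the mediation step from post-treatment to 3 months (Aim 4) are exposed.

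The SAP's main methods are valid when leaving depends only on recorded values. They are not fully valid when it also depends on worsening after the last recorded visit. If earlier data are destroyed as well, those methods lose the records they would work from.

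The direction is not fixed. If a factor works, more OFF participants leave and the difference shrinks. For data sharing it could go the other way. Section 15 names coaches as one route by which worsening is noticed, and coaches exist only with that factor ON: "When Advanced DDS with Coaches is turned OFF, participants' will not have their data shared and will not receive emails from the coaches". More detection with the factor ON would remove more of its poor responders and flatter it.

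**Working it through.** **1. The plan's own figure.** The SAP (Power Analysis) gives N = 64 for d = 0.78, four assessments, 80% power, alpha 0.05 and variance ratio 1.
- For four equally spaced visits, S = 2 × (1.5² + 0.5²) = 5.
- Reliability = 1/(1 + 1/5) = 0.833.
- Noncentrality = N × d² × reliability / 4 = 64 × 0.6084 × 0.833 / 4 = 8.11.
- Power from F(1, 62), two-sided, is 0.801, so 64 is reproduced.
- 64/0.85 = 75.3, which rounds up to 76. The plan can lose 76 − 64 = 12 people.
- Retention above 75% means more than 57 of 76, so at least 58 kept and at most 18 lost.

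**2. Who is assessed after removal.** Section 24 covers people who discontinue treatment. Sections 10, 14 and 15 speak of removal from the study or trial. No section provides assessments for people so removed.

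**3. Size of the bias.** The documents give no exit rate, so every rate here is an assumption. One million people were simulated per factor level.
- Y1 (last recorded visit) and Y2 (next visit) are normal with SD 1 and correlation r = 0.4, 0.6 or 0.8. The ON mean is −0.78 at both. The 0.78 is the SAP's planning value, stated there for change.
- A person leaves if w·Y2 + (1 − w)·Y1 plus noise exceeds a cut-off. The noise SD is k times the score's SD. The cut-off gives 3% or 5% leaving with the factor OFF.
- Y2 is regressed on Y1 and factor among those kept, then averaged over everyone randomized.

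| Case | Estimated difference (true 0.78) |
|---|---|
| Leaving depends on recorded values only (w = 0) | 0.78 |
| w = 0.5 or 1, k = 1 | 0.735-0.772 |
| w = 0.5 or 1, k = 2 | 0.760-0.776 |
| w = 0.5 or 1, sharp cut-off (k = 0) | 0.703-0.769 |
| Earlier data destroyed, complete cases, w = 0.5 or 1, k = 1 or 2 | 0.728-0.766 |
| Earlier data destroyed, complete cases, w = 0, k = 1 or 2 | 0.738-0.772 |

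The last row shows that destroying earlier data creates bias even where the planned methods would have had none.

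**4. People lost.** Assume 38 per level of each factor. At 3%, 38 × 0.03 = 1.14 OFF plus about 0.2 ON gives 1.3. At 5% with k = 2, 1.9 + 0.9 = 2.8. That is about 1-3 of 76, well inside the 12.

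**5. Opposite direction.** If coaches' notice led to 10% removed with data sharing ON and 5% OFF (assumed), the estimate is 0.79-0.83 for k = 1 or 2 and w = 0.5 or 1.

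**6. What the fix would give.** Suppose all values are collected and care elsewhere lowers binge eating by an assumed 0.5 SD. The difference over all values is then about 0.76-0.77 at 3-5% leaving.

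**The case against.** The strongest reply is that these are medical-safety exits, that few people will meet them, and that the SAP already has methods for informative missingness. Much of this stands. The higher-care rule follows a physician's finding and a meeting, so it is not a general rule for poor responders. Many triggers are weight, electrolytes or purging, which are related to binge eating frequency but are not the same thing. A shift of about 0.04 SD is under one-fifth of the standard error of a standardized difference with 76 people, √(4/76) ≈ 0.23. The SAP's sensitivity analyses can bound the problem. They cannot recover values never collected or data destroyed.

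Two stronger readings are tempting, and the documents support neither.

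- **Starting any other eating-disorder treatment means withdrawal.** A reader might join four texts: "Research participants will be withdrawn from the study if they no longer meet the study criteria"; the exclusion "Are already receiving treatment for an eating disorder"; the rule "Concurrent psychotherapy for eating pathology will not be permitted during the study as this could confound data"; and about 7 months of participation. But the exclusion is an entry criterion. Pregnancy is the only entry criterion that section 14 spells out as continuing. Applied literally throughout, the criteria would also withdraw people who improve to fewer than 12 loss-of-control episodes in 3 months, which cannot be intended. No loss should be attributed to this route.
- **Sections 10 and 15 contradict each other on sustained worsening.** The consultation in section 15 can be read as a step before the removal in section 10.

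**Conclusion.** The point holds. As written, people removed for continued worsening, for moving to higher care or for non-compliance have no stated route to later assessments, and their earlier data may be lost. That the destruction sentence reaches all these exits is likely but not explicit.

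The size is unknown and probably small. At an assumed 3-5% exit with a factor OFF, about 1-3 of 76 are lost. A true 0.78 SD is then estimated at about 0.74-0.78, at 0.70-0.77 with a sharp cut-off, or at about 0.73-0.77 from complete cases if earlier data are destroyed. These figures rest on assumed exit rates, correlations and noise. The sign is uncertain for data sharing with coaches. The documents do not support a claim of large bias or of lost power. The change is worth considering because it is cheap and uncollected outcomes cannot be recovered later. Confidence is medium.

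**What to change.** **Protocol sections 10, 14 and 15**, in matching words:

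> Continued worsening, moving to a higher level of care, or not complying with study procedures ends study treatment but does not end assessments. The reason and date are recorded. Data already collected are kept. The person is invited to the remaining assessments unless consent is withdrawn or assessment is unsafe.

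Keep the pregnancy and acute-safety stops as the sponsor sets them, named separately. State that the sentences on destroying data do not apply to the exits above. Record the start date of any other eating-disorder treatment beside the medication tracking already planned.

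**SAP**: add one sensitivity analysis that sets aside values observed after other treatment began.

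**Cost.** A few sentences and one dated field. Someone removed before mid-treatment adds at most $30 + $50 + $75 = $155 in payments, so three such people add at most $465. Assessor time comes on top; section 10 gives assessments as 3 hours. All of this is within the planned 76.

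**Downside.** Some later values will reflect other treatment, and people referred onward carry some burden. Using all values gives about 0.76-0.77 against 0.74-0.78 under the current plan, so it does not always come closer to 0.78. The gain is observed, dated values, so that both estimates can be reported.
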